A Double-Blind, Placebo-Controlled, Randomized Trial of Pentoxifylline for Imbalance

Secondary to Insufficient Microvascular Perfusion

Project #: 1214160

Version #: 2

Date: 10/14/2015

Overall and Specific Objectives:

The etiologic role of insufficient microvascular perfusion in patients with balance

disorders remains unclear. The treatment efficacy of hemorrheologic agents for imbalance has

yet to be rigorously proven. The aim of this study is to determine if pentoxifylline, which

increases perfusion at the microvascular level, improves quality of life, symptom severity, and

functionality among patients with imbalance, dizziness, and vertigo secondary to microvascular

insufficiency. Analysis of this data will permit determination of the appropriateness of

pentoxifylline use among specific diagnostic groups and create the expertise and infrastructure

for future trials among other medications and modalities for imbalance.

Background and Rationale:

The prevalence of vestibular dysfunction among American adults 40 years of age and

older is 35.4%, affecting an estimated 69 million individuals. Imbalance is even more common

among those age 65 years and older with annual incidence of dizziness of 19.6% and vertigo

present in nearly one-third of affected individuals.² The magnitude of balance dysfunction is

anticipated to expand as the number of seniors is projected to nearly double from 2005 to 2030 to

exceed 70 million individuals.³

Symptoms of imbalance have a severe impact on affected individuals with detrimental

effects on work, travel, social and family life. Large numbers of affected individuals report

1

reduced work efficiency and increased absenteeism, while up to 27% change jobs and 21% quit jobs due to their handicap. 4,5 Greater than one in four seniors, with balance disorders, suffer functional impact on exercise, shopping, driving, or social activities. Activities of daily living are compromised in 25.7% of affected elderly individuals. Limitations negatively impact autonomy, family role, work and education with an associated odds ratio for disability of 1.66. Not surprisingly, depression is correlated with dizziness and there is a significant psychological impact from fear of recurrent episodes. Dizziness and vertigo precipitate a destabilizing effect with reduced mobility resulting in deconditioning, frailty and disablement.

Falls are a significant complication of imbalance, occurring in approximately 30% of community dwelling older adults every year, with 5-10% of incidents resulting in major injuries. Higher rates of falls, affecting over two-thirds of individuals, are reported among older adults with symptoms of disequilibrium. A meta-analysis of risk factors for falling among older adults revealed that the strongest associations with falls were history of falls, gait problems, walking aid use, vertigo, Parkinson disease, and antiepileptic drug use. Older adults with disequilibrium were shown to be four times more likely to fall when compared to control subjects, and a 12-fold increase in odds of falling exists among individuals with objective vestibular dysfunction and clinical symptoms of imbalance. 1,10

Not surprisingly, imbalance prompts many visits to physicians annually. In the United States, 7.44 million patients with dizziness or vertigo were examined in ambulatory care settings between 1999 and 2000. According to the 2008 National Health Interview Survey, one-half of the 7 million individuals age 65 and older who reported dizziness or balance problems sought medical evaluation. Among those individuals, 40.6% were seen by a single provider, 59.4% by two or more providers and 36% were evaluated by three or more providers, and over 700,000

visits were made to the emergency department.¹² The cause of the balance disorder was provided to 59.6% of patients.¹² Alarmingly, only 47.9% of patients felt that their balance disorder was helped by the healthcare provider.¹² The need for improved management strategies has resulted in efforts to characterize pathologies resulting in imbalance.

Postural stability involves the accurate central integration and response to input from the vestibular, visual, and somatosensory systems. Deficits can occur within any single pathway or multiple pathways simultaneously, resulting in clinical symptoms of imbalance, dizziness and/or vertigo. Many authors have reported on the frequency of vestibular pathology with wide-ranging results depending upon the method for identification of cases, diagnostic criteria utilized, how information was gathered, and other factors. Establishment of uniform diagnostic criteria for disorders are lacking and currently under consideration by the Classification Committee of the Bárány Society. Two large studies reveal that up to 31.5% of individuals presenting to otolaryngologists with imbalance have symptoms secondary to idiopathic (including presbystasis), recurrent vestibulopathy, central vascular disorder, unknown peripheral vestibular disorder, and multisensory disequilibrium for whom inadequate evidence-based treatments are available. One of the most promising novel mechanisms of imbalance in this group is microvascular insufficiency.

Arterial flow to the inner ear is delivered by small caliber vessels in the absence of collateral blood supply. ¹⁶ The target cells, including strial marginal cells, auditory hair cells, and vestibular hair cells, are rich in mitochondria and particularly sensitive to even small perturbations in flow. ¹⁷ Transient reductions in flow are hypothesized to result in acute vestibular symptoms. Chronic hypoperfusion might result in subclinical deficits that eventually become symptomatic in isolation or synergistically with other deficits. Significant losses in spiral

ligament volume and stria vascularis volume have been demonstrated in individuals over the age of 60 as compared to those under the age of 40 years. ^{17,18} Eighty to ninety percent of individuals 70 years of age and above have evidence of semicircular canal dysfunction, 50% had abnormal saccular function and 20% had abnormal utricular function. ^{17,18} Interestingly, histologic studies show a greater loss of vestibular hair cells in the cristae ampullares of the semicircular canals relative to the otolithic maculae, suggesting that hair cell loss might be the mechanism of reduced function. ^{7,18} Human temporal bone studies and animal models support subtle and highly prevalent pathologies in the elderly, such as ischemia, as the cause of such losses with aging. ^{17,19,20} While reduction in microvascular flow to the inner ear might account for vestibular losses in some presentations, inadequate perfusion centrally can produce identical symptoms and diffuse microvascular insufficiency can lead to multisensory deficits.

Reduced blood flow to the cerebellum and lateral medulla can present as isolated vertigo, mimicking labyrinthine dysfunction and coexist with other symptomatic microvascular insufficiency. Seventeen percent of individuals with cerebral microangiopathy, in the absence of peripheral lesions, have vertigo and 31% of individuals with cerebrovascular disease experience at least one episode of isolated vertigo. Synergistic defects in multiple systems (visual, neurologic, vestibular, and central nervous system) are particularly common in older individuals and can result from microvascular dysfunction, particularly among diabetics who suffer accelerated microangiopathic effects. Therefore, reduced microvascular perfusion is a possible uniting mechanism among multiple causes of imbalance including presbystasis, multisensory losses/disequilibrium, bilateral vestibulopathy, central vascular vertigo, and peripheral vestibular hypofunction of unclear etiology. 16,19,23,24

Preliminary work/results:

Treatment efficacy with medications that improve microvascular blood flow to the inner ear is the most convincing evidence for the role of vascular insufficiency causing imbalance.

Betahistine has demonstrated efficacy for treatment of Ménière's disease and other vertiginous syndromes in randomized, placebo-controlled trials. ^{25,26} Piracetam can alleviate vertigo after head injury, vertigo in vertebrobasilar insufficiency and in peripheral vestibular disorders. ²⁷

Ginkgo biloba extract EGb 761 is effective for treatment of vestibular and non-vestibular vertigo in randomized placebo controlled trials. ²⁸ When betahistine and ginkgo biloba extract EGb 761 were directly compared in patients with peripheral vertigo not otherwise specified or vertiginous syndrome not otherwise specified similar efficacy was observed in both groups with fewer adverse effects from ginkgo biloba 761. ²⁸

Studies have also investigated the use of pentoxifylline for vascular causes of imbalance as it is known to increase erythrocyte flexibility and decrease blood viscosity, thereby improving microvascular blood flow.²⁹ Cesarone et al. performed a placebo—controlled, randomized trial, of pentoxifylline for vascular inner ear disease using a dose of 1800 mg per day and found a statistically significant increase in cochlear blood flow of 287.5% in the pentoxifylline group versus 168% in the placebo group.³⁰ Importantly, the increase in flow brought the cochlear flow in the treatment group up into the reported normal range while the placebo treated individuals flow remained reduced.³⁰ In a separate report utilizing the same patient population, Incandela et al. found a 44.1% larger reduction in symptoms including vertigo, dizziness, tinnitus, and hearing loss in the pentoxifylline group than the placebo group.³¹ In another study, Hartmann et al. studied regional cerebral blood flow, as measured by xenon 133 inhalation, among patients with reduced cerebral blood flow due to vascular disease in an open, randomized controlled, format.³² The authors found that use of pentoxifylline and the ergot alkaloid co-dergocrine

mesylate resulted in increased flow but a much more pronounced effect was seen with pentoxifylline.³² Interestingly, the pentoxifylline treated group showed preferential improvement in flow among the more ischemic brain tissue, and patients reported improvements in sleep disturbances, vertigo, and tinnitus.³² The selective improvement in flow among areas that are relatively ischemic is felt to be associated with the hemorrheologic mechanism of pentoxifylline and is proposed to be unique to drugs that work in this way without such beneficial effects in other medications such as vasodilators.³² While these reports suggest that pentoxifylline use is beneficial, small numbers of patients were included and non-validated instruments were used to measure symptomatic improvement. Therefore, further investigation into the efficacy of pentoxifylline for treatment of imbalance due to vascular etiologies is necessary, including identification of particular subsets of patients most likely to benefit from treatment. Many trials in varied populations demonstrate that pentoxifylline has an excellent safety profile with minimal increase in adverse effects over placebo making it an ideal agent to study and use if efficacy is demonstrated.^{29,30,32}

Project design and Procedures:

Adults, 18 years of age and over, presenting to the University of Missouri Department of Otolaryngology Head and Neck Surgery with chief concern of vertigo, dizziness, or imbalance will be considered for study. All individuals will undergo comprehensive clinical evaluation including otoscopic examination and testing of cerebellar function, gait observation, and dix hallpike maneuver. Additionally, all individuals will receive an audiogram and complete preintervention balance questionnaires, per standard of care. MRI of the brain/internal auditory canal as well as formal vestibular function testing will be conducted at the discretion of the enrolling provider. Individuals diagnosed with multisensory losses, presbystasis, bilateral

vestibulopathy, central vascular insufficiency, small vessel circulatory disease, generalized imbalance, and idiopathic peripheral vertigo scoring at least 16 on the Dizziness Handicap Inventory will be offered participation in the study. Patients must have sufficient English skills to complete the required surveys.

Potential participants will be excluded if any of the following diagnoses are made: benign paroxysmal positional vertigo, Ménière's disease, vestibular migraine with headache, intracranial mass, perilymphatic fistula, or multiple sclerosis. In addition, individuals will be ineligible if there is history of cholesteatoma, prior ear surgery other than myringotomy and tube placement, prior radiation therapy to the head and neck, or previous use of vestibulotoxic medications where the enrolling provider determines the drug exposure to be the cause of imbalance. Use of blood thinning medications or intolerance/allergy to pentoyifylline or methylxanthines, as well as recent cerebral or retinal hemorrhage (past 3 months), will result in exclusion. Females must not be pregnant or lactating and individuals must use adequate contraception during the study period. Females of child bearing potential will be administered a pregnancy test prior to starting the study medication.. Use of any other medications to control vertiginous symptoms and participation in vestibular rehabilitation during the study period will be prohibited.

Patients electing to participate will be randomized to receive either 400 mg of pentoxifylline three times daily for 12 weeks or placebo three times daily for 12 weeks. Allocation will be made randomly and providers and patients blinded to treatment arm. Study medications will be provided to participants at no cost, and plant cellulose will be used as placebo. Outcomes will be measured in three domains: quality of life (handicap), symptom severity, and functionality. Data will be obtained prior to initiation of therapy and at designated time intervals into treatment: 4-6 weeks and 12-14 weeks (Figure 1).

The Dizziness Handicap
Inventory will be used to assess
quality of life, the European
Evaluation of Vertigo for symptom
severity, and the Vestibular
Activities and Participation
Measure to assess functionality.
Patients will be asked to report the
number of falls in the preceding 3
months as well as document any

All patients presenting to University of Missouri Department of Otolaryngology Head and Neck Surgery with imbalance, dizziness, or vertigo will be screened according to inclusion/exclusion criteria.

All individuals meeting inclusion criteria without exclusion will be offered participation.

Patients will be randomly allocated into the active treatment or placebo group in double blind fashion.

70 "Placebo"

70 "Pentoxifylline"

4-6 weeks following treatment, patients will be reassessed. Three validated questionnaires will be completed, missed days of work tabulated, and falls recorded. Adverse effects will be documented. The assigned treatment will be continued. If inadequately tolerated dose will be reduced to twice daily.

12-14 weeks following treatment, patients will be blindly reassessed. Three validated questionnaires will be completed, missed days of work tabulated, and falls recorded. Adverse effects will be documented. Allocation will be revealed and patients will be offered to start/continue treatment with the active agent.

Figure 1: Study Design

falls during the study period. Finally, participants will be queried regarding their working status and the number of missed days due to vertiginous symptoms in the past three months prior to participation and during the study period. Head or neck imaging and vestibular function study results will be assessed by chart review at the conclusion of the study. The following adverse effects will be recorded at each clinic visit: angina/chest pain, arrhythmia/palpitation; flushing; abdominal discomfort; belching/flatus/bloating; diarrhea; dyspepsia; nausea; vomiting; agitation/nervousness; dizziness; drowsiness; headache; insomnia; tremor; blurred vision.

Medical comorbidities will be reviewed to facilitate subgroup analysis. Determination of treatment effect will be made through implementation of ANOVA testing, through IBM SPSS Statistics software.

Based upon reported data for improvement with pentoxifylline and placebo effect, at an alpha level of 0.05 and beta of 0.2, a power of 80% can be reached with 70 patients per treatment group (140 patients total).³³ We will enroll an extra 20 patients to patient dropout for a total of

160 patients to be enrolled. According to present clinic patterns, we anticipate target enrollment will be reached in approximately 18 months.

Data Handling

All data will be collected both in hard copy and electronic formats. Hard copy data will be stored in a locked office in a locked filing cabinet. Electronic data will be stored on a secure MU network drive that is encrypted and password protected. The research coordinator is responsible for access to both of these locations. Additionally, consents are signed electronically and stored on the secure network drive.

Significance of Research to the Specific Field and Stature of the University:

Vestibular dysfunction affects over one in three Americans 40 years of age and over and is more common among older individuals. Projections over the next 15 years forecast significant increases in the magnitude of imbalance, vertigo and dizziness, yet extensive diagnostic possibilities and incomplete understanding of the causes of imbalance result in 52.1% of individuals reporting that their balance problem was not helped by their healthcare provider. With evidence supporting microvascular insufficiency as a contributing or causative factor in up to one in three individuals, it warrants rigorous evaluation as a method to improve the profound negative impact of imbalance on independence, quality of life, healthcare utilization and societal contributions. Determination of efficacy will permit improved understanding of the role of microvascular insufficiency in vestibular dysfunction, and a positive finding would represent a landmark trial in medicine with the possibility to redefine the therapeutic paradigm of selected balance disorders. Effectiveness would almost certainly spark future comparative studies of other medications and modalities to treat imbalance secondary to insufficient microvascular perfusion and the University of Missouri Hearing and Balance Center would be a highly competitive site

for future external funding through grants, collaboration with pharmaceutical companies and other government agencies as a direct result of the expertise and infrastructure developed through this effort.

Resources and environment:

The Hearing and Balance Center at University Hospital and Clinics provides a steady flow of new patients meeting eligibility criteria. Potential participants will be identified by providers in the University of Missouri Department of Otolaryngology Head and Neck Surgery. The research division of the University Hospital and Clinics Pharmacy will order, prepare, and dispense study drugs according to a blinding scheme. A senior research coordinator in the Department of Otolaryngology Head and Neck Surgery will assist with patient enrollment, facilitate data collection and perform statistical testing once results are available. A resident physician within the University of Missouri Department of Otolaryngology Head and Neck Surgery will help oversee the project and facilitate completion during a 1 month dedicated research block in the 2015-2016 academic year.

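### Neither the allocation nor the ANOVA uses entry diagnosis, although seven diagnoses are pooled; a diagnosis-class factor, backed by stratified blocks, recovers a modest amount of precision almost free

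*Combined protocol and SAP*

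**What the plan says.** Three places in the combined protocol and SAP bear on allocation.

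- Project design and Procedures: "Allocation will be made randomly and providers and patients blinded to treatment arm".
- Figure 1: "Patients will be randomly allocated into the active treatment or placebo group in double blind fashion", with 70 shown under each arm.
- Resources and environment: the hospital's research pharmacy "will order, prepare, and dispense study drugs according to a blinding scheme".

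No sequence method, block size, stratification factor or minimization is given.

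Project design and Procedures makes seven diagnoses eligible: "Individuals diagnosed with multisensory losses, presbystasis, bilateral" "vestibulopathy, central vascular insufficiency, small vessel circulatory disease, generalized imbalance, and idiopathic peripheral vertigo". Each patient's diagnosis is therefore known at entry. Overall and Specific Objectives expects the analysis to settle the appropriateness of "pentoxifylline use among specific diagnostic groups and create the expertise and infrastructure". Preliminary work/results also calls for finding the subsets most likely to benefit.

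The analysis text names ANOVA in SPSS and no model terms. The only subgroup basis it names is medical comorbidity. The sample size is 70 per arm at alpha 0.05 and 80% power, with 160 enrolled to allow for dropout.

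**The concern.** The plan treats diagnosis as important: it defines who may enter and the objectives ask for answers by diagnostic group. Yet diagnosis appears in neither the allocation nor the stated analysis. If diagnosis predicts outcome, two things follow. Variation between diagnoses stays in the error term of the ANOVA, so the treatment comparison is less precise than it could be. And the mix of diagnoses may differ between arms by chance. The information needed to avoid both is collected anyway, at one site with one dispensing pharmacy.

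**Working it through.** **Inputs from the protocol.** 70 per arm, 140 in all; 160 enrolled; alpha 0.05 (taken as two-sided, since sidedness is not stated); power 80%; seven diagnoses.

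**Inputs assumed, because the protocol gives none.** Three pooled classes with shares 40/35/25; the share of outcome variance explained by class (R²) from 0 to 20%; group sizes as stated below.

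**1. The plan's own figure.** 70 per arm cannot be reproduced, because no effect size, SD or response rate is stated. Solving backwards, d = (1.960 + 0.842) × √(2/70) = 0.474, or 0.477 with the t distribution. This is a working value and does not check the plan's figure.

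**2. Gain from the class term, by formula.** With balanced classes, power = Φ(d√35 / √(1 − R²) − 1.96), and d√35 = 0.474 × 5.916 = 2.80.

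| R² | d√35 / √(1 − R²) | Power |
|---|---|---|
| 0 | 2.80 | 80% |
| 5% | 2.87 | 82% |
| 10% | 2.95 | 84% |
| 20% | 3.13 | 88% |

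**3. Separating analysis from allocation.** Simulation with 140 patients, d = 0.477 and R² = 10%, 20,000 runs per cell; ranges cover repeated simulations.

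| Allocation | No class term | Class term |
|---|---|---|
| Simple | about 79-80% | about 83-84% |
| Stratified blocks | about 81-82% | about 84% |

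Nearly all the gain comes from the class term. Given that term, stratification adds about 1 point or less. Stratifying without the term captures less than half of the gain. At R² = 0 all four cells lie at about 79-80%; the term costs two degrees of freedom.

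**4. Lopsided classes under simple allocation, 160 patients.** For a class of size m, the chance of a 2:1 or worse split is 2·P(X ≥ ⌈2m/3⌉), with X ~ Bin(m, ½).

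- Sizes 53/53/54: 0.013, 0.013 and 0.020. At least one: 1 − 0.987² × 0.980 = about 4%.
- Sizes 80/48/32: 0.002, 0.029 and 0.050. At least one: about 8%.

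**5. Overall arm sizes under simple allocation, 140 patients.** The SD of one arm's size is √(140 × ¼) = 5.9, so the 95% range is about 58 to 82. At 58:82 the information retained is 4 × 58 × 82 / 140² = 97%.

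**6. Within a single diagnosis.** An even spread gives 140/7 = 20 patients each. At 10:10, 80% power needs a difference of 2.80 × √(2/10) = 1.25 SD. At d = 0.474, power is 18% with a 10:10 split and 16% with 14:6. Variance at 14:6 exceeds that at 10:10 by (1/14 + 1/6)/(2/10) − 1 = 19%. These comparisons are weak with either split.

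**The case against.** The strongest reply is that simple randomization is valid, that ANOVA as named does not exclude a diagnosis factor, and that stratifying a trial of this size is largely a matter of preference. The protocol is also silent on the method and does not actually specify simple randomization. The 70 and 70 in Figure 1 and the phrase "dispense study drugs according to a blinding scheme" are compatible with a blocked list at the pharmacy. Nor do the documents show that diagnosis predicts outcome; the background offers microvascular insufficiency as a possible common mechanism.

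Much of this stands. There is no bias, the gain depends on an R² that nobody has stated, and stratification by itself is worth little. What remains is that a factor meant to be used should be pre-specified, and an allocation method should be written down.

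Two stronger readings are tempting and fail.

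- A reader might infer that chance imbalance does damage that no later step can repair. For the pooled test that is wrong: diagnosis is known at entry, and step 3 shows that the class term recovers nearly all of the loss.
- A reader might point to the seven diagnoses. Under simple allocation of 160 patients, the chance that at least one splits 2:1 or worse is about 52% with an even spread, and about 84% with assumed counts of 60/40/20/15/10/10/5. Those figures are correct, but they are chances for any of seven. A given diagnosis of 23 patients splits that badly about 9% of the time, and most of the 84% comes from the small groups. Stratifying on three classes would not balance seven diagnoses, and size limits those comparisons far more than the split does.

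**Conclusion.** The point holds as a cheap improvement in precision; the trial's validity is not in question. The plan leaves entry diagnosis out of both the stated allocation and the stated analysis. If three classes explain 10% of outcome variance, this costs about 4 points of power, nearly all of it recoverable through the model. If they explain none, it costs nothing. These figures rest on an assumed R², assumed class shares and a back-solved effect size.

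Stratified blocks are the secondary part. They guard against an occasional lopsided class (about 4-8% in the cases examined) and hold the arms near 70/70. The documents do not support a claim that the treatment comparison is biased, or that stratification would deliver the answers by diagnostic group that the objectives seek.

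**What to change.** 1. **Analysis.** Define about three pooled entry-diagnosis classes, for example central or small-vessel vascular; peripheral, including bilateral vestibulopathy; and multisensory, presbystasis or generalized imbalance. The investigators should confirm the grouping. Record the class before randomization and enter it as a factor in the ANOVA of treatment effect.
2. **Allocation.** State that the pharmacy allocates 1:1 by permuted blocks of randomly varying, concealed size, stratified by the same class. If a blocked list already exists, describe it.
3. **Order of priority.** If only one change is made, make the first. Stratifying without the factor gives up much of the benefit.

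The cost is a sentence or two of protocol text, a pharmacy list with three strata and one model term. There are two practical burdens. The provider must name the class before the next allocation is drawn. Block sizes must vary and stay with the pharmacy, because Figure 1 has allocation revealed at 12-14 weeks while enrollment is expected to run for about 18 months, so opened codes could otherwise make later allocations guessable.

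### Three unranked scales at two visits have no primary outcome, visit or success rule; if any one scale may be claimed, familywise error is about 8–14%, not 5%

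*Combined protocol and SAP*

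**What the plan says.** Overall and Specific Objectives asks whether pentoxifylline, which "increases perfusion at the microvascular level, improves quality of life, symptom severity, and" functionality. The three aims are joined and none is ranked above the others.

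Project design and Procedures repeats the list: "Outcomes will be measured in three domains: quality of life (handicap), symptom severity, and functionality". It assigns the Dizziness Handicap Inventory (DHI) to the first domain, the European Evaluation of Vertigo to the second and the Vestibular Activities and Participation Measure to the third. All three are completed before treatment and at 4–6 and 12–14 weeks. Falls and missed work days are also recorded.

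The analysis plan is a single sentence: "Determination of treatment effect will be made through implementation of ANOVA testing", using SPSS. On subgroups it says: "Medical comorbidities will be reviewed to facilitate subgroup analysis". On sample size it says that "at an alpha level of 0.05 and beta of 0.2, a power of 80% can be reached with 70 patients per treatment group". That statement rests on a cited source, and no outcome, effect, SD or response rate is given.

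The DHI is singled out only for eligibility (a score of at least 16). No section names a primary outcome, a primary visit, a success rule or a multiplicity adjustment.

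**The concern.** The section on the significance of the research says that "a positive finding would represent a landmark trial in medicine", but nothing defines a positive finding. With three co-equal scales and two visits, the headline result can be chosen after the data are seen. The unspecified subgroup analysis adds another route to a selective claim.

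The stated alpha and power cannot both be taken at face value until a rule exists:

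- If success on any one scale is enough, the 5% is too low.
- If success on all three is required, the 80% is too high, provided it refers to each scale separately.
- A single global test could respect both figures, but none is described.

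Timing makes this more pressing. At the 12–14 week visit in Figure 1, "Allocation will be revealed and patients will be offered to start/continue treatment with the active agent". That suggests patients are unblinded one by one while the trial is still running, so a rule written late would be hard to defend as independent of the data.

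**Working it through.** **Inputs from the document.** Alpha 0.05 (sidedness not stated; two-sided assumed); power 80%; 70 per arm, 140 in total, 160 enrolled; three scales; two post-baseline visits.

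**Assumed, not in the document.** The correlation between scales, and between visits, taken from 0 to 0.9.

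**The plan's own figure.** The 70 per arm cannot be reproduced forwards, because no outcome, effect or SD is given. Solving backwards for a difference in means:

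d = (1.960 + 0.842) × √(2/70) = 0.474 SD by the normal approximation, or 0.477 SD with the t distribution.

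Seventy per arm would equally fit responder proportions that differ by about 22–24 points, such as 50% against 73%. The enrolment total is consistent with 12.5% dropout: 160 × (1 − 0.125) = 140.

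**Rule A: any one scale suffices.** With three independent tests at 0.05, the familywise error is 1 − 0.95³ = 0.143. For correlated scales, equicorrelated normal test statistics were simulated under no effect (critical value 1.96, 4,000,000 draws).

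| Correlation between scales | At least one significant, either direction | At least one false claim of benefit |
|---|---|---|
| 0 | 14.3% | 7.3% |
| 0.3 | 13.6% | 6.8% |
| 0.5 | 12.6% | 6.3% |
| 0.7 | 10.9% | 5.5% |
| 0.8 | 9.8% | 4.9% |
| 0.9 | 8.4% | 4.2% |
| Nominal | 5% | 2.5% |

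The inflation is 8.4/5 = 1.7-fold to 14.3/5 = 2.9-fold. The benefit-only column gives the same ratios (4.2/2.5 = 1.7 and 7.3/2.5 = 2.9).

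**Upper case: each scale also tested at each visit.** Six independent tests give 1 − 0.95⁶ = 26.5%. With scale and visit correlations both 0.5 the figure is 21.9%; with both 0.9 it is 11.5%. The plan neither states nor excludes this.

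**Rule B: all three scales must succeed.** Familywise error stays at or below 5%. If each scale has 80% power, joint power with independent scales is 0.8³ = 51%; the other values are simulated. The last column is the effect per scale that 70 per arm would need for 80% joint power, against 0.48 SD for a single scale.

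| Correlation | Joint power | Effect needed per scale |
|---|---|---|
| 0 | 51% | 0.58 SD |
| 0.5 | 61% | 0.56 SD |
| 0.8 | 69% | 0.53 SD |
| 0.9 | 72% | 0.52 SD |

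**Rule C: one global test on the average of the three scales.** At 0.477 SD per scale, power is 99.8%, 92.9%, 85.3% and 82.6% at correlations 0, 0.5, 0.8 and 0.9, with alpha held at 5%.

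**The case against.** The strongest reply is that the plan never says one scale is enough. Read literally, the objective joins the three domains with a conjunction, which suggests all must improve, and on that reading alpha is not inflated. This is fair: the error figures are conditional on an any-scale rule. But the conjunction states an aim and is no decision rule. Under the strict reading the problem moves to power.

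Several narrower points also stand:

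- Zero correlation is implausible for three questionnaires about one condition, so 14.3% is an outer bound. Even at 0.9 the error is well above 5%.
- A repeated-measures ANOVA could merge both visits into one test per scale. The 8–14% range already counts only three tests, so it does not depend on the visits.
- For an efficacy claim, the relevant absolute risk is the benefit-only one, about half the two-sided figure. The relative inflation is unchanged.
- The SD figures presume a comparison of means, whereas the sample size may have come from responder proportions. They are illustrative.
- Preliminary work/results says of earlier pentoxifylline reports that "non-validated instruments were used to measure symptomatic improvement". This does not show that the 80% is wrong for the chosen scales, because the sample size cites a different reference. What stands is simpler: the text gives no outcome, effect or SD to which the 80% could be attached.

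None of these supplies the missing primary outcome, visit or rule.

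**Conclusion.** The concern holds and must be fixed. The omission is certain: the relevant sentences are intact in the document and none defines what the trial has to show. Its size depends on the rule eventually adopted.

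An any-scale claim with one unadjusted two-sided test per scale carries about 8–14% familywise error, or 4.2–7.3% against 2.5% for false claims of benefit. An all-scales claim leaves 51–72% joint power if 80% applies to each scale. Both ranges rest on assumed correlations of 0 to 0.9. Separate tests at each visit, the other endpoints or subgroup tests would raise the any-scale figure further.

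**What to change.** 1. Name one primary outcome and visit, for example the between-arm difference in DHI at 12–14 weeks, tested at two-sided 0.05. The DHI is only a suggestion; the choice is the sponsor's.
2. Only if that test is significant, test the other two scales at 12–14 weeks, in a stated fixed order or by Holm.
3. Report the 4–6 week results, falls, missed work days, and the comorbidity and diagnostic-group analyses as supportive, with confidence intervals. The diagnostic groups need naming here because the objectives also promise conclusions about them.
4. Restate the power for the chosen outcome with a justified between-arm effect and SD. Seventy per arm gives 80% power for about 0.48 SD, so the sample need not grow if that effect can be justified.

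If the sponsor prefers to keep three equal claims, a Bonferroni split (0.05/3 = 0.0167 each) at 0.474 SD leaves 65.8% power per scale with 70 per arm, and needs 94 per arm for 80%.

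The recommended change costs a short amendment and one justified effect and SD, with no new data collection. It should be made before outcomes are reviewed by arm, ideally before the first patient's allocation is revealed. The price is that a positive result on a secondary scale alone can no longer be claimed as the trial's success.
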